10.7 BODY SURFACE AREA CALCULATION

The target dose of Afatinib has been calculated based on BSA derived from the Dubois and Dubois formula.

$$BSA = (W^{0.425} \times H^{0.725}) \times 0.007184$$

Whereas:

W is the weight is in kilograms

H is the height is in centimetres.

The paediatric dose was calculated as follows:

Dose child = Dose adult x (BSA child / BSA adult) considering BSA = 1.75 m² for adult

Proprietary confidential information.

© 2017 Boehringer Ingelheim International GmbH or one or more of its affiliated companies. All rights reserved.

This document may not - in full or in part - be passed on, reproduced, published or otherwise used without prior written permission.

10.8 EXAMPLE FOR FORMULA APPROPRIATE FOR GFR ESTIMATION IN CHILDREN

Please use the modified Schwartz-formula below or your institutional standard formula appropriate for GFR estimation in paediatric patients. In case GFR measurements are available, these may replace GFR estimation.

$$eGFR = k \times L / Scr$$

whereas:

eGFR is estimated GFR in millilitres per minute per $1.73m^2$

L is height in centimeters

Scr is serum creatinine in milligrams per decilitre

k is 0.45 for term infants throughout the first year of life, 0.55 for children and adolescent girls and 0.7 for adolescent boys

Note that the Cockcroft-Gault formula is not suitable to estimate GFR in paediatric patients

Proprietary confidential information.

© 2017 Boehringer Ingelheim International GmbH or one or more of its affiliated companies. All rights reserved.

This document may not - in full or in part - be passed on, reproduced, published or otherwise used without prior written permission.

11. DESCRIPTION OF GLOBAL AMENDMENT(S)

Number of global amendment		1
Date of CTP revision		04 May 2015
EudraCT number		2014-002123-10
BI Trial number		1200.120
BI Investigational Product(s)		Giotrif®, Gilotrif®, Afatinib Capsules and Solvent for Oral Solution
Title of protocol		Phase I open label, dose escalation trial to determine the MTD, safety, PK and efficacy of afatinib monotherapy in children aged 2 years to <18 years with recurrent/refractory neuroectodermal tumours, rhabdomyosarcoma and/or other solid tumours with known ErbB pathway deregulation regardless of tumour histology
To be implemented only after approval of the IRB/IEC/Competent Authorities		 applies to optional CSF PK sampling
To be implemented immediately in order to eliminate hazard – IRB / IEC / Competent Authority to be notified of change with request for approval		
Can be implemented without IRB/IEC/ Competent Authority approval as changes involve logistical or administrative aspects only		 applies to clarification for P-gp modulators
Section to be changed		
 1. Flow-Chart 2. Abbreviations 3. Section 1.2 4. Section 4.2.3.1 5. Section 5.5 6. Section 7.3.5 7. Appendix 10.3 8. Appendix 10.4
Description of change		
 1. Add optional CSF PK sampling 2. Add CSF 3. Additional details on handling of strong P-

Proprietary confidential information.

© 2017 Boehringer Ingelheim International GmbH or one or more of its affiliated companies. All rights reserved.

This document may not - in full or in part - be passed on, reproduced, published or otherwise used without prior written permission.

Number of global amendment		1
		gp inhibitors/inducers provided 4. Same as change 3 5. Same as change 1 6. Same as change 1 7. Same as change 1 8. Same as change 3
Rationale for change		Changes 1, 2, 5, 6, 7 : To assess afatinib penetration into the CSF Changes 3, 4, 8: Clarification that the use of strong P-gp inhibitors/inducers is prohibited during course 1 of dose finding to assure that MTD definition is not affected by potential co-administration of strong P-gp inhibitors/inducers. Additional details are given on how to use strong P-gp inhibitors/inducers with afatinib if their use cannot be avoided after course 1 of the dose finding part and how to handle them during MTD expansion cohort.

Number of global amendment		2
Date of CTP revision		18 Aug 2016
EudraCT number		2014-002123-10
BI Trial number		1200.120
BI Investigational Product(s)		Giotrif®, Gilotrif®, Afatinib Capsules and Solvent for Oral Solution
Title of protocol		Phase I open label, dose escalation trial to determine the MTD, safety, PK and efficacy of afatinib monotherapy in children aged 2 years to <18 years with recurrent/refractory neuroectodermal tumours, rhabdomyosarcoma and/or other solid tumours with known ErbB pathway deregulation regardless of tumour histology
To be implemented only after approval of the IRB/IEC/Competent Authorities		
To be implemented immediately in order to eliminate hazard – IRB / IEC / Competent Authority to be notified of		

Proprietary confidential information.

© 2017 Boehringer Ingelheim International GmbH or one or more of its affiliated companies. All rights reserved.

This document may not - in full or in part - be passed on, reproduced, published or otherwise used without prior written permission.

Number of global amendment change with request for approval		2
Can be implemented without IRB/IEC/ Competent Authority approval as changes involve logistical or administrative aspects only		
Section to be changed		
 1. Flow-Chart, Section 4.1.2, 4.2.1, 5.2.2, 6.2.1 and 6.2.2 2. Section 6.2.1 3. Section 6.2.2 4. Section 1.2, 2.3, 5.2.2.1, 8.4.1 and 9.2
Description of change		
 1. Clarification on the possible use of a pre-screening informed consent for the collection and testing of tumour tissue sample 2. Clarification on how to manage collection of tumour images during the screening period 3. Alignment of the section with Flow Chart 4. Deletion of IB version reference
Rationale for change		
 1. Clarification 2. Clarification 3. Clarification - correction of typo and omission 4. Clarification to always refer to the most recent IB version
Number of global amendment		3
Date of CTP revision		02 June 2017
EudraCT number		2014-002123-10
BI Trial number		1200.120
BI Investigational Product(s)		Giotrif®, Gilotrif®, Afatinib Capsules and Solvent for Oral Solution
Title of protocol		Phase I/II open label, dose escalation trial to determine the MTD, safety, PK and efficacy of afatinib monotherapy in children aged ≥1 years to <18 years with recurrent/refractory neuroectodermal tumours, rhabdomyosarcoma and/or other solid tumours with known ErbB pathway deregulation regardless of tumour histology
To be implemented only after approval of the		

Proprietary confidential information.

© 2017 Boehringer Ingelheim International GmbH or one or more of its affiliated companies. All rights reserved.

This document may not - in full or in part - be passed on, reproduced, published or otherwise used without prior written permission.

Number of global amendment		3
IRB/IEC/Competent Authorities		
To be implemented immediately in order to eliminate hazard – IRB / IEC / Competent Authority to be notified of change with request for approval		
Can be implemented without IRB/IEC/ Competent Authority approval as changes involve logistical or administrative aspects only		
Section to be changed		
 1. Synopsis 2. Flow Chart 3. Section 1 (1.1 and 1.2) 4. Section 2 (2.1, 2.2, 2.3) 5. Section 3 (3.1, 3.2, 3.3) 6. Section 4 (4.1.2, 4.1.3, 4.1.4, 4.2.2.3, 4.2.3) 7. Section 5 (5.1, 5.2.1, 5.3.1, 5.4, 5.5.1, 5.5.3, 5.6-5.6.1) 8. Section 6 (6.2.1, 6.2.2, 6.2.3) 9. Section 7 (7.1, 7.3.1, 7.3.2, 7.3.5, 7.6) 10. Section 9 (9.1, 9.2) 11. Section 10 (10.1, 10.3)
Description of change		
 1. Multiple changes for adaptive Phase I/II design 2. Same as 1 3. Same as 1 and literature update 4. Same as 1 5. Same as 1 6. Same as 1, literature update and update on contraception methods 7. Same as 1 8. Clarification on pre-screening informed consent use/editorial changes 9. Same as 1 10. Addition of literature references 11. Same as 1 and clarification on alternative PK samplings
Rationale for change		Changes 1 to 7, 9, 11: to reflect changes necessary to comply with the Written Request received from FDA

Proprietary confidential information.

© 2017 Boehringer Ingelheim International GmbH or one or more of its affiliated companies. All rights reserved.

This document may not - in full or in part - be passed on, reproduced, published or otherwise used without prior written permission.

Number of global amendment		3

2. LIST OF ABBREVIATIONS

Term	Definition / description
AE	Adverse event
AUC	Area Under Curve
BMI	Body mass index
BRPM	Blinded report planning meeting
BSA	Body surface area
BUN	Blood urea nitrogen
C _{max}	Maximum Concentration
CR	Complete Response
CTC	Common Terminology Criteria
CTP	Clinical Trial Protocol
CTR	Clinical Trial Report
DLT	Dose Limiting Toxicity
DM&SM	Boehringer Ingelheim Data Management and Statistics Manual
DoR	Duration of objective response
DRA	Drug Regulatory Affairs
EMA	European Medicines Agency
FAS	Full analysis set
FDA	Food and Drug Administration
ICH	International Conference on Harmonisation
INRC	International Criteria for Neuroblastoma Response Criteria
IPD	Important protocol deviation
LVEF	Left ventricular ejection function
MedDRA	Medical Dictionary for Regulatory Activities
MQRM	Medical Quality Review Meeting
MTD	Maximum Tolerated Dose
MxR	Mixed response
NOR	Not-valid results
NOS	No sample available
NR	No response
O*C	Oracle Clinical
OR	Objective Response

Term	Definition / description
PD	Progressive Disease
PFS	Progression free survival
PK	Pharmacokinetics
PopPK	Population Pharmacokinetic(s)
PPS	Per protocol set
PPSR	Proposed pediatric study request
PR	Partial Response
PSTAT	Project Statistician
PT	Preferred term
Q1	Lower quartile
Q3	Upper quartile
SAS	Statistical Analysis System
s.d.	Standard deviation
SD	Stable Disease
SMQ	Standardised MedDRA query
SOC	System Organ Class
t_{\max}	Time to reach maximum concentration
TCM	Trial Clinical Monitor
TMW	Trial Medical Writer
TOC	Table of contents
TSAP	Trial Statistical Analysis Plan
TSTAT	Trial Statistician
VGPR	Very good partial response

3. INTRODUCTION

As per ICH E9 (1), the purpose of this document is to provide a more technical and detailed elaboration of the principal features of the analysis described in the protocol and its amendments, and to include detailed procedures for executing the statistical analysis of the primary and secondary variables and other data.

This Trial Statistical Analysis Plan (TSAP) assumes familiarity with the Clinical Trial Protocol (CTP), including Protocol Amendments. In particular, the TSAP is based on the planned analysis specification as written in CTP Section 7 “Statistical Methods and Determination of Sample Size”. Therefore, TSAP readers may consult the CTP for more background information on the study, e.g., on study objectives, study design and population, treatments, definition of measurements and variables, planning of sample size, randomization.

SAS[®] Version 9.4 will be used for all analyses.

4. CHANGES IN THE PLANNED ANALYSIS OF THE STUDY

The clinical trial protocol (CTP) v3 was amended based on the feedback received from the FDA during a PPSR request. The MTD expansion cohorts will now recruit up to 38 patients evaluable for OR based on biomarker selection criteria as well as specific tumour indications.

The definition of duration of objective response was misspecified in the CTP as the interval between the date of randomization and the earliest date of disease progression. The correct definition is clarified in [Section 5.2.2](#) of this TSAP as the time from first documented response of CR, VGPR, PR, or MxR until the earliest of disease progression or death among patients with objective response.

5. ENDPOINT(S)

5.1 PRIMARY ENDPOINT(S)

Dose finding part:

- The primary endpoint is the **dose limiting toxicity** (DLT) measured during the first course of treatment. DLTs are defined in Table 4.1.4.1.2 of the CTP.
- **Pharmacokinetics** ($AUC_{\tau,ss}$, $C_{max,ss}$)

The primary objective of the dose finding part is to determine the maximum tolerated dose (MTD) of the study drug as defined by patients with DLT in a paediatric population. The MTD will be determined as the highest dose at which no more than 1/6 patients experienced DLT. The MTD evaluation period is defined as the initial 28 days of study treatment. Patients who developed DLT at any time during the initial 28 treatment days and patients who have completed the MTD evaluation period without missing more than 25% of the afatinib doses regardless of the reason will be referred to as patients evaluable for DLT.

MTD expansion cohort part:

- **Objective response** (OR) by investigator assessment according to the institutional response evaluation criteria for the given tumour type, assessed every 8 weeks until progression of disease.

5.2 SECONDARY ENDPOINT(S)

5.2.1 Key secondary endpoint(s)

There were no key secondary endpoints for this study.

5.2.2 Secondary endpoint(s)

Dose finding part:

- **Objective response** (OR) assessed by investigator according to the institutional response evaluation criteria for the given tumour type, assessed every 8 weeks until progression of disease
- **Pharmacokinetics** (AUC_{0-24} , C_{max} , $t_{max(ss)}$ and accumulation (or effective) half-life)

MTD expansion cohort part:

- **Progression free survival** (PFS) is defined as the duration of time from the date of first drug administration to the date of the first documented disease progression evaluated according to institutional response criteria or to the date of death from any cause, whichever occurs first. Censoring rules and dates of outcome for PFS under difference scenarios are specified in [Table 5.2.2: 1](#).
- **Duration of objective response** (DoR) is defined as the time from first documented response of CR, VGPR, PR, or MxR until the earliest of disease progression or death among patients with objective response. Censoring rules and dates of outcomes follow the same specifications as for PFS in Table 5.2.2: 1 for applicable scenarios.
- **Pharmacokinetics** ($AUC_{\tau(ss)}$, $C_{max(ss)}$, $t_{max(ss)}$ and accumulation (or effective) half-life)

Table 5.2.2: 1 Censoring rules and determination of date of event or censoring for PFS

Situation	Outcome (event or censored)	Date of outcome
No baseline radiological assessment (no death before second scheduled radiological assessment)	censored	Date of first treatment administration
Death without progression. At most one missed radiological assessments, i.e. at most 112 days between death and last assessment (or treatment start date if no post-baseline assessments).	event	Date of death
Death without progression. Two or more missed radiological assessments, i.e. longer than 112 days between death and last assessment (or treatment start date if no post-baseline assessments).	censored	Date of last radiological assessment / Date of first treatment administration if no post-baseline assessments
No radiological assessment performed post-baseline, vital status is unknown or patient is known to be alive	censored	Date of first treatment administration
Progressed according to radiological assessment. At most one missed radiological assessments, i.e. at most 112 days between progression and last assessment before progression.	event	Date of radiological assessment of progression
Progressed according to radiological assessment, i.e. longer than 112 days between progression and last assessment before progression.	censored	Date of last radiological assessment before progression
Alive and not progressed (irrespective of missed radiological assessments)	censored	Date of last radiological assessment
Initiation of subsequent anti-cancer therapy		
Subsequent anti-cancer therapy started before progression or death	censored	Date of last radiological assessment before subsequent anti-cancer therapy
No baseline and/or post-baseline imaging and subsequent anti-cancer therapy started prior to a death	censored	Date of first treatment administration

For further details on endpoints, please see CTP Section 5.

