 - 13 Imaging (CT or MRI for CNS tumours or soft tissue lesions) assessment is to be performed every 8 weeks until progression of disease. In case of objective response, the latter has to be confirmed 4 to 6 weeks after initial OR observation. Consecutive imaging assessment will be performed every 8 weeks. In exceptional cases when patients have been stable on treatment for at least 2 consecutive images (i.e. 16 weeks), imaging intervals may be extended to 12 weeks upon discussion between the investigator and the sponsor.
 - 14 Tumour marker(s) in urine or blood as indicated depending on tumour type (e.g. catecholamines (VMA/HVA, dopamine), NSE in neuroblastoma)
 - 15 Intra-patient dose escalation might be allowed as soon as the next higher dose tier is completed and considered safe (applicable to dose finding part only). A dose reduction can also be applied in case of drug-related toxicity (see [Section 4.1.4.3](#))
 - 16 New kit(s) of trial drug must be dispensed at visit 1 of each course. If needed (e.g. in case a dose adaptation has to be applied during treatment course), new kit(s) of trial drug might be dispensed outside of the planned visit schedule
 - 17 A full PK profile (extensive PK sampling) is to be taken at course 1, day 1: pre-dose before afatinib administration then 1h, 2h, 3h, 4h, 5h, 6h, 8h and 24h after administration and to be repeated at steady state on day8. In exceptional cases where extensive PK sampling is not possible, a limited sampling approach must be applied with blood sampling before, 1h and 3 h after afatinib administration. An additional trough sample is to be taken on day 15 to confirm steady state exposure to afatinib. In addition, trough CSF sampling (from Rickham, Ommaya reservoirs or from lumbar puncture performed for clinical reasons not related to the trial) may be taken on day 8 or later. This CSF sampling is optional. Each trough CSF sample has to be accompanied by a trough plasma sample taken at the same time-point. For further details on time points and sampling volumes, see [Section 5.5.2](#) and [Appendix 10.3](#).
 - 18 During the dose escalation part, a DLT confirmation fax has to be sent to the sponsor before start of course 2.
 - 19 AE/SAE after the 28-30 days FU period have to be reported only if considered relevant by the investigator.
-
- 22 Lansky for patients ≤ 12 years or Karnofsky for patients older than 12 years at time of informed consent

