3.3.4 Removal of patients from therapy or assessments

3.3.4.1 Removal of individual patients

The Investigator, patient and/or parent/legal guardian may stop study treatment at any time for safety or personal reasons.

If a patient is entered in violation of inclusion/exclusion criteria, the sponsor, in discussion with the investigator and if needed DMC, will determine the medical benefit/risk on a patient-by-patient basis and can require such a patient be discontinued from the study treatment.

A patient is to discontinue study medication if:

- 1 The patient and/or parent/legal guardian withdraw assent/consent to continue therapy without the need to justify.
- 2 The patient is no longer receiving benefit from treatment, in the opinion of the investigator.
- 3 In the investigator's medical judgment, further participation would not be in the best interest of the patient, or might be injurious to the health and well-being of the patient
- 4 The patient is no longer able to participate for other medical reasons (e.g. surgery, adverse events, secondary malignancy, or other diseases)

Proprietary confidential information.

© 2017 Boehringer Ingelheim International GmbH or one or more of its affiliated companies. All rights reserved.

This document may not - in full or in part - be passed on, reproduced, published or otherwise used without prior written permission.

- 5 A female post-menarchal patient becomes pregnant ([Section 5.2.2.3](#))
- 6 The patient is diagnosed with ILD, keratitis or heart failure (including clinically relevant LVEF reduction) ([Section 4.2.1](#))
- 7 The patient needs further dose reductions considered necessary but not allowed according to the protocol ([Section 4.1.4.3](#))

The sponsor may remove patients from the study after completion of the primary analysis and grant access to afatinib via an alternative source e.g. through an expanded-access program, named patient use program, or compassionate use protocol.

Patient discontinuation of study participation:

A patient, who has discontinued study medication, will complete a follow-up (FU) visit 28-30 days after the last intake of the trial drug. After this FU visit, no further study procedure will be performed and the patient will enter the observation period during which only data collection on (S)AE(s) considered relevant by investigator, vital status and further anti-cancer treatment will be requested.

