6.2.3 End of treatment and follow-up period

End Of Treatment visit

This visit will take place as soon as a decision is made to permanently discontinue trial treatment.

The EOT visit will include the following actions:

Repeated procedures	Physical examination and vital signs; blood sampling for safety lab; update on concomitant therapies and adverse events
---------------------	---

Proprietary confidential information.

© 2017 Boehringer Ingelheim International GmbH or one or more of its affiliated companies. All rights reserved.

This document may not - in full or in part - be passed on, reproduced, published or otherwise used without prior written permission.

Ophthalmological examination	To exclude keratitis
Pulmonary examination	To exclude ILD
Pregnancy test	To be performed in post-menarchal female patients who are of childbearing potential
Performance score	Lansky for patients \leq 12 years or Karnofsky for patients older than 12 years at time of informed consent
Cardiac assessment	
 • LVEF echocardiography • 12 lead-ECG as detailed in Section 5.2.4
Assessment of the tumour disease	Depending on the tumour type, an assessment of the tumour disease has to be reported in the eCRF based on: 
 ○ imaging findings ○ tumour markers in blood or urine if indicated ○ clinical findings ○ bone marrow if indicated
Patient diary	Check for completion
Compliance check	Check on trial drug compliance
Conclusion of treatment	To confirm permanent treatment discontinuation

Follow-up visit for safety (28-30 days after last afatinib intake)

Safety update	Update on concomitant therapies and adverse events
Conclusion of patient participation	Confirmation of trial discontinuation for the patient

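### SAP Table 5.2.2:1 has no event row for non-radiological progression, although the PFS definition is not limited to imaging; some documented progressors are censored, which can overstate PFS

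*SAP*

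**What the plan says.** **Definition.** SAP 5.2.2 runs PFS from first drug administration to "first documented disease progression evaluated according to institutional response criteria or to the date of death from any cause". Nothing there limits progression to imaging. Protocol 5.1.1.2 censors event-free patients at their latest adequate assessment of the tumour, again without naming radiology.

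**Event table.** The only progression row in SAP Table 5.2.2:1 that yields an event begins "Progressed according to radiological assessment. At most one missed radiological assessments". A second radiological row censors progression found after a gap of more than 112 days. Other rows that matter here:

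- "No radiological assessment performed post-baseline, vital status is unknown or patient is known to be alive": censored at first dose.
- Death without progression: an event at the date of death if within 112 days of the last assessment, or of treatment start when there is no post-baseline assessment. Otherwise censored at the last scan, or at first dose if there is none.
- New anti-cancer therapy before progression or death: censored at the last scan before that therapy.
- "No baseline and/or post-baseline imaging and subsequent anti-cancer therapy started prior to a death": censored at first dose.

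**Data collected.** For the end-of-treatment (EOT) visit, Protocol 6.2.3 states: "Depending on the tumour type, an assessment of the tumour disease has to be reported in the eCRF based on" imaging, tumour markers, clinical findings and bone marrow. Protocol 5.2.2.1, in its exemptions from SAE reporting, recognises clinical signs of progression whether or not imaging confirms them, and sends progression to the efficacy pages of the eCRF. Protocol 3.3.4.1 lets treatment stop when the investigator sees no further benefit.

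**Follow-up.** Flow chart footnote 13 says imaging "assessment is to be performed every 8 weeks until progression of disease". The flow chart also schedules imaging at EOT, within 7 days of the last dose. Protocol 3.3.4.1 then says: "After this FU visit, no further study procedure will be performed and the patient will enter the observation period".

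**The concern.** The definition and the table that implements it disagree. Take a child whose progression is documented on clinical, marker or marrow grounds but not on a scan. The text makes that child an event; the table has no row that does. Two programmers could code the same child differently, and the one who follows the table will usually censor.

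A patient censored because the investigator has just recorded progression is not exchangeable with those still under observation, so Kaplan-Meier's assumption of non-informative censoring fails in a known direction. The setting makes such cases plausible: scans are 8 weeks apart, and Protocol 1.1 cites survival of 4-6 months from relapse in high-grade glioma. In a single-arm trial PFS is read at face value, with no control arm to share the bias.

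The narrowing is also undeclared. SAP section 4, which lists changes to the planned analysis, does not mention it.

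**Working it through.** **Step 1: the plan's own figure.** The 112-day window for at most one missed scan is two 8-week intervals: 2 x 8 x 7 = 112 days. It reproduces.

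**Step 2: trace one patient through the table.** Suppose progression is documented on day 35 (week 5) on clinical, marker or marrow grounds. The definition in SAP 5.2.2 gives an event on day 35 if the institution's criteria accept that progression. Table 5.2.2:1 gives:

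| Post-baseline scan | What follows | Table 5.2.2:1 |
|---|---|---|
| None | Alive, or status unknown | Censored at first dose |
| None | New therapy, then death (say day 98) | Censored at first dose |
| None | Death after day 112, no new therapy | Censored at first dose |
| None | Death by day 112, no new therapy | Event, dated at death |
| EOT scan, no progression seen | Alive, or new therapy starts | Censored at EOT scan |
| EOT scan shows progression | Any | Event at that scan |

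In the second line the death falls within 112 days, so the death row could also apply. I read the more specific new-therapy row as taking precedence; the SAP does not state the order.

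**Step 3: direction.** Let N be the number of patients, E the true failures by week 8, and k the failures censored before the first counted event. With the remaining failures counted at the week-8 scan, Kaplan-Meier gives

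S = 1 - (E - k)/(N - k) = (N - E)/(N - k).

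This exceeds the true (N - E)/N whenever k > 0 and E < N. It does not matter whether the k patients leave on day 1 or at an EOT scan before week 8: either way they are out of the risk set when the first event is counted.

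**Step 4: illustration.** N = 38 comes from Protocol 3.3 (up to 38 expansion patients). True week-8 PFS and k are assumptions; the documents give neither.

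- True PFS 15/38 = 39.5%: k = 0 gives 39.5%; k = 4 gives 15/34 = 44.1%; k = 8 gives 15/30 = 50.0%.
- True PFS 11/38 = 28.9%: k = 2 gives 11/36 = 30.6%; k = 8 gives 11/30 = 36.7%.
- True PFS 19/38 = 50.0%: k = 2 gives 19/36 = 52.8%; k = 8 gives 19/30 = 63.3%.
- True PFS 27/38 = 71.1%: k = 2 gives 27/36 = 75.0%; k = 8 gives 27/30 = 90.0%. Here k = 8 means 8 of 11 failures, an extreme case.

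**The case against.** The strongest reply is that the table and visit schedule already catch most of these patients. Much of it stands, and it rules out several stronger readings.

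- **A reader might infer that the fastest clinical progressors are all censored on day 1.** They are not. An unscanned patient who dies within 112 days of treatment start without new therapy is an event. The event is late, not lost, and short survival makes that row more likely to apply.
- **A reader might infer that tumour assessment stops with treatment.** Imaging is scheduled at EOT, so a compliant early stopper has a post-baseline scan. If it shows progression there is no bias; if not, censoring is at that scan rather than at first dose. What is missing is any planned tumour assessment after the follow-up visit.
- **A reader might take the illustrated gap as an estimate.** It is not. The baseline PFS and k are both assumed, and k = 0 is possible. The 38 are patients evaluable for response, so unscanned patients may come on top of that number.
- **A reader might extend the day-1 problem to duration of response.** A responder already has a post-baseline assessment, so those rows hardly apply. The SAP limits the carry-over to applicable scenarios and only lists DoR when fewer than 5 patients respond.
- **A reader might count patients who stop for toxicity as part of the same bias.** Censoring a progression-free patient at the last scan does not by itself push PFS up.

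The institutional criteria are not in the documents, and every expansion patient needs a measurable lesion. How often those criteria accept non-radiological progression therefore cannot be checked. None of this supplies the missing row.

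**Conclusion.** The point holds in limited form. The PFS definition admits progression under institutional criteria, and the table that applies it recognises radiological progression only. Followed as written, the table censors some documented progressors, at first dose or at the EOT scan, and dates some others at death. Where this happens the censoring is informative and Kaplan-Meier PFS moves upward.

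The size is unknown. It depends on how many patients progress without radiological evidence, whether the EOT scan is done and what it shows, and how many die early without new therapy. The illustration runs from no effect at k = 0 to about 10 points (39.5% to 50.0%) at k = 8, on assumed inputs.

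PFS is secondary and descriptive, with no hypothesis test (Protocol 7.2). The primary endpoint, the sample size and error rates are untouched. It should still be corrected, because the published PFS curve would otherwise not follow its own definition.

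**What to change.** 1. In SAP Table 5.2.2:1, add an event row for documented progression under the institutional response criteria, including clinical, marker or bone-marrow progression where those criteria allow it, dated at that documentation.
2. State that this row takes precedence over the rows for no post-baseline imaging and for new therapy when the progression was documented first. State also the order between the death row and the new-therapy rows.
3. Keep radiology-only PFS as a sensitivity analysis. If radiology-only PFS was what the sponsor intended, correct the definition in SAP 5.2.2, declare it in SAP section 4, and make the institutional-criteria version the sensitivity analysis.
4. Separately, reconcile flow chart footnote 13 (imaging until progression) with Protocol 3.3.4.1 (no study procedure after the follow-up visit).

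Items 1 to 3 cost SAP wording and one extra programmed analysis. The protocol already directs progression to the efficacy pages of the eCRF, and no scans are added. The drawback is that clinical progression dates are softer than scan dates; the radiology-only analysis shows how much that matters. Collecting progression dates at the 12-weekly post-trial contacts is not needed for this repair: it would require a protocol amendment and give unsystematic dates.
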